9.2.3 Patient Selection

9.2.3.1 Inclusion Criteria

Patients will be included in the study if they meet the following inclusion criteria:

- Age ≥18 years old at index date

AND

(

- Patients with at least one hospital stay with a principal (PD), related (RD) or associated (AD) diagnosis (in PMSI-MSO) of code I48 (Atrial fibrillation of the International Classification of Disease 10th version, ICD-10) or with an active Long-Term Disease (LTD) with ICD-10 code I48 during the study (historical or inclusion) period

AND/OR

- Patients who are new users of OACs for the AF treatment with or without AF diagnosis (PMSI-MSO or LTD), identifying with a validated and published algorithm with a high specificity (c-index 0,93), using a predictive model developed by Billonnet et al. (16).

)

Description of the algorithm:

The algorithm for identifying patients exposed to OAC indicated for AF will be based on the patients who receive at least one reimbursement of an OAC (VKA, apixaban, rivaroxaban or dabigatran) during the inclusion period, without use of any OAC in the 24 months prior to the first reimbursement date.

Patients reported with at least one orthopedic procedure (osteoarticular or muscular) of the lower limb (including hip/knee replacement) as corresponding to the indication of primary prevention of venous thromboembolic events, during a 6-week period before the first date of OAC delivery will be excluded.

Then, three groups of patients will be identified:

- Confirmed AF are defined as patients with at least one hospital stay with a PD, RD or AD of code I48 or with an active LTD with ICD-10 code I48 or with an electrical cardioversion procedure or radiofrequency ablation before the first date of OAC delivery during the historical period;
- Confirmed DVT/PE are defined as patients hospitalized with a diagnosis of PE (code I26 in any position) or DVT (codes I80 except I80.0, I81, I82 in any position) or with a doppler ultrasound examinations, CT venography, MR venography or pulmonary scintigraphy during a 6-week period before the first date of OAC delivery;
- Unclassified patients in other cases.

Patients with both confirmed AF and DVT/PE will be excluded.

Then, a logistic model included 14 independent covariables will be applied on unclassified patients to identify AF outpatients. The model will include following covariables: age, gender, use of treatments as use of beta-blockers, antiarrhythmics, antihypertensive drug, holter/echocardiography procedures, cardiologist prescriber, D-dimer blood test reimbursement and presence of hospitalization for arterial thromboembolic event.

Finally, for each unclassified patient, those with a predicted probability above the cut-off value providing specificity of 95% (sensitivity: 63%), will be assumed to be AF outpatients.

9.2.3.2 *Exclusion Criteria*

Patients will be excluded from the study if they meet any exclusion criteria:

- Patients with at least one hospital stay with an ICD-10 code in PD, RD or AD for associated valve disease, ICD-10 codes I05 to I09, I34 and I39, or valve surgery;
- Standard SNDS exclusion criteria (e.g. unicity of identifier not guaranteed, twins, aberrant demographic data, beneficiaries from Mayotte overseas French territory).

[figure not shown]

Figure 2. AF study population according to inclusion and non-inclusion criteria

9.2.3.3 *Populations*

Two populations of AF patients will be considered for analyses according to study objectives:

9.2.3.3.1 *Prevalent AF population*

Prevalent AF patients will be defined as patients diagnosed with AF during the historical period.

Prevalent AF population will be considered for the following analysis:

- To estimate the annual prevalence of patients with non-valvular AF, exposed and unexposed to OAC (objective 4).

9.2.3.3.2 *Incident AF population*

Incident AF patients will be defined as patients newly diagnosed with AF (i.e. no AF diagnostic during the historical period) from January 1st, 2016 to December 31st, 2019 (inclusion period), and to December 31st (2020 for sensitivity analyses).

For incident AF population, two datasets of incident AF patients will be considered for the following analyses:

- For longitudinal analyses: objectives 1, 2, 3 and 7 (cf. 8. Objectives)

Inclusion of patients with:

- An AF newly diagnosed during inclusion period

AND

- No reported events of interest (stroke, major bleeding, and death) within 30 days before index date (i.e. for patients for whom the date of inclusion is not the date of the first dispensation of OA) (cf. 9.2.3.1. Inclusion Criteria)
- For cross-sectional analyses (objectives 2, 4, 5 and 6) and analysis for exploratory objective (objective 8):
 - Inclusion of patients with:
 - An AF newly diagnosed during inclusion period.

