Parameter	Description/Definition
Sociodemographic characteristics	Age, sex, complimentary universal health care (CMU-c), aid for complementary health care (ACS) for elderly patients, department of patient's residence
Medical history and comorbidities	Identified algorithmically with hospital diagnoses, active long-term disease, drugs and medical procedures: Coronary arterial diseases (CAD), Dementia (Alzheimer dementia/vascular dementia/other dementia), Ischemic or hemorrhagic stroke (intracranial bleeding) Congestive Heart failure, Peripheral arterial disease, Other vascular diseases; Sleep disorders; Active cancer (within 6 months in the historical period) Age adjusted Charlson Cormordity Index (ACCI) adapted to the SNDS data (20) ; Frail patient identified by Claims-Based Fragility Index (CFI) adapted to the SNDS data (21) ; Malnutrition ; Morbid Obesity; Anemia; COPD Diabetes Patients at risk of falls identified by an algorithm adapted to SNDS data (22) ; Patients poly-medicated Patient with at least one nursing home entry available
Drug exposure	AF patients exposed to VKA, apixaban, rivaroxaban, dabigatran AF patients unexposed to OAC
Associated treatments	Beta-blockers, antihypertensives, antiplatelet drugs, other anticoagulants, Non-steroidal anti-inflammatory drugs (NSAIDs), oral corticoids, proton pump inhibitors, Selective serotonin reuptake inhibitor antidepressants (SSRIs), systemic azole antifungals, medical procedure of cardioversion, CYP P450 inhibitors, protease inhibitors
Left atrial appendage (LAA) occlusion	Medical procedure of treatment of thromboembolic risk in AF in alternative of OAC
Modified risk scores in AF	Thromboembolic risk: Modified CHA ₂ DS ₂ VASC identified by an algorithm adapted to SNDS data Hemorrhagic risk: Modified HAS-BLED identified by an algorithm adapted to SNDS data

Parameter	Description/Definition
Annual standardized incidence rate of AF	Ratio of number of newly diagnosed non valvular AF patients to the number of individuals in the French population per calendar year (N per 100,000 inhabitants) standardized on age using the 2019 French population structure and 2020 in sensitivity analyses.
Annual prevalence of AF	Ratio of number of diagnosed NVAF patients to the number of individuals in the French population (INSEE data) per calendar year (N per 100,000 inhabitants).

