9.2.1.2 Index Date

Depending on the date of first evidence of AF over the study period, AF patients will be included at the following dates:

- On 1st January 2016 for **prevalent AF patients** (i.e., patients diagnosed AF during the historical period);
- On the first date of evidence of AF (first date of diagnosis of AF identified either by a LTD or the start date of a hospitalization, or the first date of OAC dispensation) for **incident AF patients**.

A patient will be considered exposed to OAC at the time of his/her inclusion if at least one dispensation of OAC is issued within 30 days after inclusion (including date of inclusion). In such a case, the index date will be the date of the first dispensation of OAC (cf. Appendix 1).

Otherwise, if no dispensation of OAC will be identified within 30 days from inclusion, the index date will be the date of inclusion.

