9.2.1.3 Historical period

The historical period is a period of 2 years before the index date in order to distinguish incident and prevalent AF-patients, describe patient's comorbidities, medical history and history of treatments. Consequently, this historical period starts from January 1st, 2014.

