9.4.3.2 Comparison of the incidence of stroke, major bleeding, death

The incidence rate ratio for each event of interest (stroke, major bleeding and death; see [Table VIII](#) for derivation of events of interest) will be compared using a Cox regression model with OAC exposure (see [Table VII](#) for derivation of exposure sequences) considered as time-dependent variable adjusted for covariates. Covariates will be derived at index date as indicated in [Table XV](#).

Table XV. Derived variables for confounders

Variable	Definition
Age	Categorical variable (<80 years old / 80–90 / >90 years old) See Table III
Sex	Binary variable (Female / Male) See Table III
Prescriber's specialty at initiation of OAC	Categorical variable (Hospital-based physician/ City cardiologist/ Generalist practitioners/Other) See Table III
Having Malnutrition	Binary variable (Yes / No) See Table III
Risk of falls	Binary variable (Yes / No) See Table III
Frail patients	Binary variable (Yes / No) See Table V
Morbid obesity	Binary variable (Yes / No) See Table VI
At least one visit to a nursing home	Binary variable (Yes / No) See Table VI
Concomitant treatments	Binary variable (Yes / No) for each concomitant treatment listed in Table XIV

For example, for antiplatelet drugs, equals to “Yes” if the patient has at least one reimbursement for an antiplatelet drug in the 4 months before the index date
	
HAS-BLED score	Categorical variable (0, 1, 2, 3, ≥ 4) See Table VI
CHAD₂DS₂VASC score	Categorical variable (0, 1, 2, 3, 4, ≥ 5) See Table VI
Age adjusted Charlson Cormordity Index (ACCI) adapted to SNDS data	Categorical variable (0, 1-2, 3-4, ≥ 5) See Table VI XII

9.4.3.3 *Estimation of the AF annual standardized incidence rate and prevalence*

All the variables in [Table XVI](#) will be derived for all AF patients in France in 2016, 2017, 2018 and 2019.

Table XVI. Derived variables for incidence and prevalence

Variable	Definition
Incident AF patient	Binary variable (Yes / No) See Table X
Prevalent AF patient	Binary variable (Yes / No) Equals to “Yes” if the patient is diagnosed AF during the historical period Patients belonging to the study population

9.4.3.4 *To describe the use of oral anticoagulants (OACs) in AF patients initiating treatment (AF patients exposed to OAC therapy)*

Table XVII. Derived variables for OAC treatment pattern

Variable	Definition

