Name of the analysis	To estimate the incidence rate of stroke (ischemic or hemorrhagic), major bleeding and death in both AF patients (exposed and unexposed to OAC)	To describe the characteristics of AF patients exposed and unexposed to OAC	To compare the incidence rate of stroke, major bleeding, and death between those two populations	To estimate the annual incidence and prevalence of patients with AF, exposed and unexposed to OAC	To describe the use of oral anticoagulants (OACs) in AF patients initiating treatment (AF patients exposed to OAC therapy)	To compare the Healthcare Resource Utilization (HCRU) and associated costs between patients exposed to apixaban, rivaroxaban, dabigatran, VKA and patients unexposed to OACs	To describe the therapeutic management before/after the first stroke occurring after initiation of OAC exposure	To identify subgroups among AF patients with similar profile
Outcomes	Estimation of the incidence rate of stroke, major bleeding, and death. Incidence rate in unexposed patients will be standardized on age using the exposed to OAC group as population of reference.	Description of sociodemographic characteristics, comorbidities, medical history of interest and concomitant treatments	Comparison of incidence rate in longitudinal analysis for each event of interest (stroke, major bleeding, and death)	Estimation of the annual incidence and prevalence of patients with AF. Annual incidence will be standardized on age using INSEE data (French population) as population of reference	Description of the use of oral anticoagulants (OACs) in AF patients initiating treatment (AF patients exposed to OAC therapy)	Comparison of the Healthcare Resource Utilization (HCRU) and associated costs between patients exposed to apixaban, rivaroxaban, dabigatran, VKA and patients unexposed to OACs	Description of the therapeutic management before/after the first stroke occurring after initiation of OAC exposure	Identification of subgroup of AF patients with similar profile

Periods	2016 - 2019	2016-2019 (per calendar year)	2016 - 2019	2014 – 2019 (per calendar year)	2016 - 2019	2016 - 2019	2016 - 2019	2016 - 2019
Populations	Incident AF patients	Incident AF patients	Incident AF patient	All AF patients (prevalent & incident)	Incident AF patients exposed to OAC	Incident AF patients exposed and unexposed to OAC	Incident AF patients exposed to OAC	Incident AF patients exposed and unexposed to OAC

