9.7.4.3 Estimation of the annual standardized incidence rate and prevalence

The analysis of annual standardized incidence rate and prevalence of diagnosed AF patients in France in 2016, 2017, 2018 and 2019 will be descriptive in nature and will be performed for each calendar year, from 2016 to 2020.

Prevalent and incident patients with an AF diagnosis will be the patients with a diagnosed NVAF during the historical period and the patients newly diagnosed AF during the inclusion period. The estimations of the prevalence and incidence of AF will be based on the count of patients living in France as denominator (based on socio-demographic data published by the National Institute for Statistics and Economic Studies (INSEE) and will be expressed per 100,000 inhabitants.

The analysis will include the following measures for summarizing the information on the prevalence and incidence of diagnosed AF patients, for each calendar year between 2016 and 2019 in France:

- Overall count of prevalent and incident of diagnosed AF patients in year Y, separately
- Overall crude prevalence and cumulative incidence of diagnosed AF patients in year Y, separately; computed as:

$$CP_Y = \frac{\text{count of prevalent diagnosed NVAF patients in year Y}}{\text{count of French adult residents from census data in year Y}} \times 100,000$$

- CP_Y represents the crude prevalence of diagnosed AF patients in the year Y
- Y represents the year of interest

$$CI_Y = \frac{\text{count of incident diagnosed NVAF patients in year Y}}{\text{count of patients at risk in year Y}} \times 100,000$$

- CI_Y represents the cumulative incidence of diagnosed NVAF patients in the year Y
- Y represents the year of interest
- *Count of patients at risk* represents French adult residents from census data in year Y minus count of prevalent diagnosed NVAF patients in year Y

- Overall age-standardized cumulative incidence of diagnosed AF patients in year Y computed as:

$$age - SCI_Y = \frac{\sum_i CI_{i,Y} \times N_{i,Y}}{\sum_i N_{i,Y}} \times 100,000$$

- $age - SCI_Y$ represents the age-standardized cumulative incidence of diagnosed AF patients in year Y
- i represents the age group (<65 years old / 65-74 / 75-79 / \geq 80 years)
- Y represents the year of interest
- $CI_{i,Y}$ represents the crude cumulative incidence of diagnosed AF patients in the age group i in the year Y

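### Annual prevalence (secondary objective 4) is tied to AF diagnosed in the historical period, so patients first diagnosed from 2016 on are left out of the 2016-2019 counts, contrary to the protocol's definition

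*SAP*

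**What the plan says.** Four places in the SAP set the operational definition.

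- **9.2.3.3.1:** "Prevalent AF patients will be defined as patients diagnosed with AF during the historical period". This population is then assigned to one analysis: "To estimate the annual prevalence of patients with non-valvular AF, exposed and unexposed to OAC (objective 4").
- **9.2.1.2:** the inclusion date is "On 1st January 2016 for prevalent AF patients (i.e., patients diagnosed AF during the historical period"). On the historical period itself, 9.2.1.3 adds: "Consequently, this historical period starts from January 1st, 2014". For these patients the period is therefore 2014-2015.
- **Table XVI (9.4.3.3):** a single flag for 2016, 2017, 2018 and 2019, set to yes "if the patient is diagnosed AF during the historical period".
- **9.7.4.3:** the same split is repeated (historical period for prevalent, inclusion period for incident). The crude prevalence CP_Y is the count of prevalent patients in year Y over adult residents. The at-risk denominator of the cumulative incidence CI_Y is "French adult residents from census data in year Y minus count of prevalent diagnosed NVAF patients in year Y".

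Three places describe a different numerator.

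- **Protocol Appendix 1, indicative study parameters:** "Ratio of number of diagnosed NVAF patients to the number of individuals in the French population (INSEE data) per calendar year".
- **SAP abstract, secondary objective 4:** also all diagnosed non-valvular AF patients per calendar year.
- **SAP Table XXI (9.7.1), populations for objective 4:** "All AF patients (prevalent & incident").

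**The concern.** Annual prevalence, overall and by anticoagulant exposure, is half of secondary objective 4. SAP 9.2.3.3.2 defines incident patients by the absence of AF in the historical period, so the two groups exclude each other and nobody moves from incident to prevalent. A prevalence series built this way follows one closed group. It cannot show how many people live with diagnosed AF in 2017, 2018 or 2019, and it leaves out the patients first diagnosed around and after the 2018 recommendations whose effect the study wants to describe. Two programmers working from different sections of the same SAP would deliver different versions of Table A13.

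**Working it through.** The documents give no expected prevalence for this analysis, so there is no planned figure to reproduce. The check traces the definition and then sizes the effect.

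**1. Trace one patient.** Take a patient first diagnosed in March 2016 and alive through 2019.

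| Rule | Result |
|---|---|
| SAP 9.2.1.2 and 9.2.3.3.2 | Enters as incident in March 2016 |
| SAP Table XVI flag | Not prevalent (no AF in 2014-2015) |
| SAP CP_2016 to CP_2019 | Never counted |
| SAP CI_2017 to CI_2019 denominator | Not subtracted, so still counted as at risk |
| Protocol, SAP abstract | Counted in 2016 and in every later year |

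**2. Trend of the closed group.** Let m be annual mortality. The documents do not give it, so 5%, 10% and 15% are assumed. With a constant population, CP_2019 / CP_2016 = (1 - m)^3, whatever the starting count:

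- m = 5%: 0.95^3 = 0.857, a fall of 14%
- m = 10%: 0.90^3 = 0.729, a fall of 27%
- m = 15%: 0.85^3 = 0.614, a fall of 39%

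If the adult population grows by an assumed 0.5% a year, each ratio is divided by 1.005^3 = 1.015, and the falls become about 16%, 28% and 40%. If deaths are not removed, the numerator is constant and the ratio moves only with the denominator: 0%, or about -1.5% with that growth.

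**3. Patients left out.** SAP 9.5 gives 225,747 new anticoagulant users with AF in 2018. At a constant number per year, 3 x 225,747 = 677,241 would be first identified in 2016-2018, before deaths. These are new users rather than new diagnoses, so the figure indicates order of magnitude only.

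**4. Incidence denominator.** SAP 7.1 gives a standardized rate of 410 per 100,000 for 2018. The implied population is 225,747 / 0.00410 = about 55.1 million, which is approximate because the rate is standardized. Earlier incident cases not subtracted, before deaths:

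- 2017: 225,747 / 55.1 million = 0.41%
- 2018: 451,494 / 55.1 million = 0.82%
- 2019: 677,241 / 55.1 million = 1.23%

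CI_Y is too low by about these proportions overall. The share will be larger in the oldest age bands, where AF concentrates.

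**5. Would accumulating all evidence since 2014 be enough?** Start from two years of new users (2 x 225,747 = 451,494), add a constant 225,747 a year and apply mortality: P(Y+1) = (P(Y) + 225,747)(1 - m). Per 100,000 at 1 January of 2016, 2017, 2018 and 2019:

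- m = 5%: 820, 1168, 1500, 1814
- m = 10%: 820, 1107, 1365, 1598
- m = 15%: 820, 1046, 1237, 1400

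Inflow is constant, yet the series rises by 71% to 121% because case capture lengthens. The illustration overstates the effect, since active long-term-disease status also picks up diagnoses made before 2014, but the direction is clear.

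**The case against.** The best defence is that the intended measure is plain. Table XXI names prevalent and incident patients together, the title of Table A13 speaks of all AF patients, the abstract and protocol use all diagnosed patients, CP_Y is indexed by year, and 9.2.1.3 defines the historical period relative to the index date. The cross-sectional dataset in 9.2.3.3.2 also lists objective 4. The affected output is descriptive; the primary objective, the Cox models, the treatment patterns and the costs use incident patients.

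As evidence of intent and as a limit on the damage, this stands. It does not repair the definition. Objective 4 covers incidence as well as prevalence, so naming incident patients there does not place them in the prevalence numerator. The relative historical period does not help, because 9.2.1.2 fixes a single entry date for all prevalent patients. The analysis section itself repeats the fixed split.

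Three stronger readings are tempting, and the documents do not support them.

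- **Prevalence must fall every year.** This needs deaths to leave the count. Indexing by year suggests it, but no rule says so.
- **A definite share of true prevalence is captured.** One could take 1% of 66 million (660,000) and add new users. SAP 7.1 puts valve disease at more than one-third of AF patients, so the non-valvular stock on these figures is below about 440,000, and adding treated inflow to an arbitrary stock makes the comparator rise by construction.
- **The exposure split misses everyone treated after 2018.** SAP 9.7.4.3 sets exposure year by year, so a patient diagnosed in 2014-2015 and treated in 2019 counts as exposed in 2019. Only patients newly diagnosed from 2016 are missed.

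**Conclusion.** The point holds as a conflict between the SAP's operational definition and the measure stated in the protocol, the SAP abstract and Table XXI. That CP_Y omits patients first diagnosed from 2016 on follows from the text alone and needs no assumption. The shape of the resulting series depends on a death rule that the SAP does not give: flat without one, or about 14% to 39% lower in 2019 than in 2016 with one, at assumed annual mortality of 5% to 15% and a constant population. The effect on incidence is small, about 1% of adults by 2019. The consequence is confined to secondary objective 4, but there the 2016-2019 prevalence outputs would not measure what the protocol defines.

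**What to change.** In 9.2.3.3.1, Table XVI and 9.7.4.3, replace the single flag with one per calendar year. A patient is prevalent in year Y if both conditions hold:

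- there is qualifying non-valvular AF evidence (hospital I48, active long-term disease I48, or the anticoagulant algorithm) within a look-back of the same length for every year, for example 1 January of Y-2 to 31 December of Y;
- the patient is alive and under follow-up in year Y, with the SAP stating whether this is judged at a date or over the year.

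These windows lie within the 2014-2020 extraction. One detail needs stating. The algorithm requires 24 months without an anticoagulant, which cannot be verified before January 2016 in data that start in January 2014, and Table II applies it to the inclusion period only. Algorithm-only cases therefore fill the window only from 2018. The analysis without the algorithm, already planned in 9.7.6, has a constant look-back throughout and should be read beside the main series.

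If all evidence since 2014 is accumulated instead, capture grows from 3 years for 2016 to 6 years for 2019. Report that series only alongside the fixed look-back series, and say that its trend is inflated.

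For CI_Y, subtract from census adults the living patients with AF evidence before 1 January of year Y.

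The cost is SAP wording and a year-specific flag, with no new data. The downside is that a fixed look-back misses patients with no recent AF evidence, so the prevalence should be reported as a lower bound.
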